11.0 INTERIM ANALYSIS

At the time of preparation for the Protocol Addendum Amendment 2, a blinded interim analysis was performed as part of data quality review as the study was progressing. In this review, it was observed that the standard deviation for the primary and secondary endpoints were substantially lower than the originally assumed values for sample size calculations. The observed standard deviations in the blinded reviews of this study and other ongoing acute studies at the same time (RAP-MD-01, and RAP-MD-02) were taken into considerations for revising the sample size estimation in next section (Determination of Sample Size).

RESTRICTED

12.0 DETERMINATION OF SAMPLE SIZE

The originally proposed primary efficacy variable is the change from baseline (ie., Day 7) at Day 8 in MADRS total score and the primary analysis population included the subset of patients who were placebo non-responders during the placebo lead-in period before randomization. Based on that the study was planned to randomize 700 patients (including both placebo responders and placebo non-responders), assuming standard deviation (SD) of 10 points, which provides 99% power to detect a difference of 3.25 points in MADRS total score between rapastinel 450 mg and placebo at a 2-sided significance level of 0.05.

While the study was ongoing, the primary efficacy variable was revised to be the change from baseline in MADRS score at the last visit, Day 21, and the primary efficacy study population was revised to include all randomized patients (placebo responders and placebo non-responders) based on the feedback by the FDA, EMA, and PDMA. Both of these changes were included in Amendment 2 of the protocol. At the same time of Amendment 2, a blinded data review was conducted for Studies RAP-MD-01, RAP-MD-02, and RAP-MD-03. The pooled SD for the three studies were 7.4, 8.0, and 8.7, respectively, all smaller than the originally assumed 10 points. Sample size was re-calculated using 8.7 as the common SD. The calculation used MMRM model with simulations; it also assumed correlation of 0.5 between the repeated measures and a common drop-out rate of 10% during the randomized treatment period and an additional 5% drop-out rate during the placebo lead-in period for all treatment groups. To have 90% power, the total sample size required is 360 patients. However, the study had already enrolled more than 390 patients with less than 5% of overall drop-out rate, surpassing the re-estimated sample size of 360 patients. The study enrollment was halted as soon as operationally feasible. The final sample size is approximately 420 patients (210 patients per treatment group).

13.0 STATISTICAL SOFTWARE

Statistical analyses will be performed using [REDACTED]

RESTRUCTURED

14.0 DATA HANDLING CONVENTIONS

14.1 VISIT TIME WINDOWS

Table 14.1–1 presents visits assigned and the corresponding range of treatment days (window) during which an actual visit may occur for all safety analyses where baseline is the last nonmissing assessment before the first dose of DB IP in the placebo lead-in period. The visit windows used in the “change from Day 0” or “reduction from Day 0” efficacy analyses will be derived according to this table as well. Termination visit is assigned to the visit window according to the table below.

Table 14.1–1. Visit Time Windows for Change from Day 0 in Efficacy and Change from Baseline in Safety Analyses

Analysis Visit	Target Date	Analysis Window (Based on Date)
Baseline	Index0 ^a	Last record on or before Index0 ^a
Day 1	Index0 ^a +1	Index0 ^a +1
Day 4	Index0 ^a +4	[Index0 ^a +2, IndexA ^b -1]
Day 7	IndexA ^b	IndexA ^b
Day 8 ^d	IndexA ^b +1	IndexA ^b +1
Day 11	IndexA ^b +4	[IndexA ^b +2, IndexB ^c -1]
Day 14	IndexB ^c	IndexB ^c
Day 15 ^d	IndexB ^c +1	IndexB ^c +1
Day 18	IndexB ^c +4	[IndexB ^c +2, IndexB ^c +5]
Day 21 ^{de}	IndexB ^c +7	Days [IndexB ^c +6, day of final double-blind visit or Early-termination Visit occurring after IndexB ^c +5]
Day 28	IndexB ^c +14	Within the safety follow-up phase

a Index0: Date of placebo dose during the placebo lead-in period

b IndexA: Date of first randomized dose or Index0 + 7 for patients who did not receive any randomized dose

c IndexB: Date of second randomized dose or IndexA + 7 if the 2nd dosing of randomized treatment was not administered for patients who were randomized

d For analysis of parameters BPRS+ (Brief Psychiatric Rating Scale) and CADSS (Clinician Administered Dissociative States Scale), the visit windows for Days 1 and 8 will be extended to cover the next dosing day (indexA and indexB, respectively); the visit window for Day 15 will be 1 day after IndexB to Day 19; and the visit window for Day 21 will be Days 20 to the last double-blind visit, inclusively.

For efficacy analysis where baseline is defined as the last measurement prior to the first dose of randomized IP, the assigned visit and the corresponding range of treatment days (window) during which an actual visit may occur is displayed in **Table 14.1–1**. Termination visit is assigned to the visit window according to the table below.

Table 14.1–2. Visit Time Windows for Change from Baseline in Efficacy Analyses

Analysis Visit	Target Date	Analysis Window (Based on Date)
Day 0	Index0 ^a	Last record on or before Index0 ^a
Baseline	IndexA ^b	Last record on or before IndexA ^b
Day 8	IndexA ^b +1	IndexA ^b +1
Day 11	IndexA ^b +4	[IndexA ^b +2, IndexB ^c -1]
Day 14	IndexB ^c	IndexB ^c
Day 15	IndexB ^c +1	IndexB ^c +1
Day 18	IndexB ^c +4	[IndexB ^c +2, IndexB ^c +5]
Day 21 ^e	IndexB ^c +7	Days [IndexB ^c +6, day of final double-blind visit or Early-termination Visit occurring after IndexB ^c +5]
Day 28	IndexB ^c +14	Within the safety follow-up phase

a Index0: Date of placebo dose during the placebo lead-in period

b IndexA: Date of first randomized dose or Index0 + 7 for patients who did not receive any randomized dose

c IndexB: Date of second randomized dose or IndexA +7 if the 2nd dosing of randomized treatment was not administered for patients who were randomized

If a patient has 2 or more non-missing assessments within the same window, the assessment closest to the target day will be used for analysis; if there are 2 closest assessments with the same number of days from the scheduled day, the later one will be used for analysis.

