**9.1.2****Double-blind Treatment Period**

Approximately 700 patients are planned for enrollment in the double-blind treatment period (350 patients each in the rapastinel 450 mg and placebo groups). Patients will be randomized in a ratio of 1:1 to 1 of 2 treatment groups: rapastinel 450 mg IV weekly or placebo IV weekly (both adjunctive to ongoing ADT).

During the double-blind treatment period, patients will have 3 study visits per week. The visits will occur in the following pattern: treatment day, 1 day following the treatment day, 4 days following the treatment day, and 7 days following the treatment day (which is the next treatment day). If necessary, study visits may be conducted up to 2 days before or after the scheduled visits with the exception of visits that are 24 hours apart (eg, Visits 2 and 3 must be conducted 1 day apart; similarly, Visits 5 and 6 as well as Visits 8 and 9 must be conducted 1 day apart). All patients who receive IP must complete Visit 11. Upon completion of the double-blind treatment period, patients are eligible to enter the RAP-MD-04 maintenance study. Patients who do not enter RAP-MD-04 will enter a 1-week safety follow-up period.

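### SAP Table 14.1-1 footnote d sets the Day 15/Day 21 boundary for BPRS+ and CADSS at Days 19/20, so after an early second randomized dose a Visit 11 rating can be filed under Day 15

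*SAP*

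**What the plan says.** SAP section 14.1 assigns safety assessments to analysis visits through Table 14.1-1. The rows that matter here are counted from the second randomized dose, which the table defines as "IndexB: Date of second randomized dose or IndexA + 7 if the 2nd dosing of randomized treatment was not administered". Day 15 is IndexB+1, Day 18 runs from IndexB+2 to IndexB+5, and Day 21 starts at IndexB+6 with target IndexB+7. The day count itself starts from the lead-in dose ("Index0: Date of placebo dose during the placebo lead-in period").

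Footnote d replaces some of these windows for BPRS+ and CADSS. For the early visits it stays with dose dates: "the visit windows for Days 1 and 8 will be extended to cover the next dosing day (indexA and indexB, respectively"). For the later ones it says "the visit window for Day 15 will be 1 day after IndexB to Day 19". The Day 15 window therefore has a start that moves with the dose and an end given as a plain day number. The footnote treats the final visit in the same way, with a plain day number at its start: "the visit window for Day 21 will be Days 20 to the last double-blind visit, inclusively".

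When several ratings fall in one window, section 14.1 says that "the assessment closest to the target day will be used for analysis". On scheduling, Protocol section 9.1.2 describes visits by their distance from the treatment day and says that "study visits may be conducted up to 2 days before or after the scheduled visits", except for the visit pairs that must be one day apart.

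**The concern.** A permitted shift of the second randomized dose moves every IndexB boundary in the table but not Days 19 and 20. The two sets of boundaries then part. A Visit 11 rating that the table body places in Day 21 can fall inside the footnote's Day 15 window. There it competes with the rating taken the day after the dose, and the closest-to-target rule removes it from the by-visit summary, leaving that patient without a Day 21 value.

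BPRS+ and CADSS cover psychotomimetic and dissociative effects, the domain in which Protocol section 7.0 contrasts rapastinel with ketamine. What is at stake is whether the end-of-treatment summary of these two scales is complete and correctly labelled.

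**Working it through.** **Inputs.** Windows, footnote d and the closest-to-target rule: SAP 14.1. Dosing at Visits 2, 5 and 8: Protocol 9.4.7, matched to Index0, IndexA and IndexB. Visit 9 one day after Visit 8, Visit 11 seven days after Visit 8, 2-day tolerance: Protocol 9.1.2.

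**1. Nominal schedule.** Index0 = Day 0, IndexA = Day 7, IndexB = Day 14. Then IndexB+5 = 14+5 = Day 19 and IndexB+6 = 14+6 = Day 20. The footnote's figures are reproduced exactly, and no visit is misfiled.

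**2. Early second dose, Visit 11 on Day 19 (21-2, within tolerance).**

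| IndexB | Visit 9 | Visit 11 | Table body | Footnote d as written | Footnote d re-anchored |
|---|---|---|---|---|---|
| Day 12 | Day 13 | Day 19 = IndexB+7 | Day 21 | Day 15 | Day 21 |
| Day 13 | Day 14 | Day 19 = IndexB+6 | Day 21 | Day 15 | Day 21 |

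The Day 15 target is IndexB+1. Visit 9 is 0 days from it; Visit 11 is 6 days away in the first row and 5 in the second. Visit 9 is kept, and Day 21 has no value. With IndexB on Day 13 and Visit 11 a full 7 days later, on Day 20, filing is correct.

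**3. How often.** The documents give no distribution of visit dates. Assumption: each shift is independent, with probabilities for (-2, -1, 0, +1, +2) days of (0.03, 0.07, 0.80, 0.07, 0.03) in a looser case and (0.015, 0.035, 0.90, 0.035, 0.015) in a tighter one.

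*Tolerance around calendar days.* The share is P(Visit 11 on Day 19) × P(IndexB on Day 12 or 13).
- Looser: 0.03 × (0.03+0.07) = 0.0030.
- Tighter: 0.015 × (0.015+0.035) = 0.00075.

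This is 0.08-0.3%.

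*Tolerance accumulating from dose to dose.* IndexB = 14+e1+e2 and Visit 11 = IndexB+7+e3. A rating is misfiled when Visit 11 is on or before Day 19 and at IndexB+6 or later. Looser case:
- IndexB = 12: (2×0.03×0.80 + 0.07²) × (0.07+0.80) = 0.0529 × 0.87 = 0.0460
- IndexB = 13: (2×0.07×0.80 + 2×0.03×0.07) × 0.07 = 0.1162 × 0.07 = 0.0081
- IndexB = 11: (2×0.03×0.07) × 0.94 = 0.0039
- IndexB = 10: 0.03² × 0.97 = 0.0009

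The sum is 0.059. The same steps in the tighter case give 0.0264 + 0.0022 + 0.0010 + 0.0002 = 0.030. This is 3.0-5.9%.

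**4. Re-anchored text.** With Day 15 as IndexB+1 to IndexB+5 and Day 21 from IndexB+6, a Visit 11 rating at IndexB+7 goes to Day 21 for every IndexB from Day 10 to Day 18. When IndexB is Day 14 the windows are identical to the current ones.

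**5. Late second dose.** With IndexB on Day 15 and Visit 11 on Day 20 (IndexB+5), or IndexB on Day 16 and Visit 11 on Day 20 or 21 (IndexB+4 or +5), the table body says Day 18, the footnote as written says Day 21, and the re-anchored footnote says Day 15.

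**The case against.** **Days 19 and 20 may be shorthand.** In the table, Day 14 is simply the name for IndexB and Day 15 the name for IndexB+1. Carried on, Day 19 would mean IndexB+5 and Day 20 IndexB+6, which are the table's own cut-points. This may well be what was meant. But the SAP does not say so, neither day is an analysis visit in the table, and the same sentence uses IndexB where it means a dose date. The reading makes the defect one of wording; it does not remove it.

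**It may hardly ever happen.** A reader might infer that the second dose is often off Day 14 and that a dozen or more patients are affected. The documents do not support that. The tolerance is stated around scheduled visits, and on that reading the share is 0.3% or less even under the assumed rates. The 3-6% needs tolerance that accumulates across doses.

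**Other harms one might infer.** One is that a late rating may stand in for a next-day rating; another is that one visit carries different labels for different safety parameters. Both come largely from the footnote's deliberate design: it extends Days 1 and 8 to the next dosing day and lets Day 15 absorb the Day 18 range. Re-anchoring leaves both in place.

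**Downstream use is not visible.** The visit-level schedule and the analysis text for these scales are redacted. That a Day 21 rating and by-visit summary exist is inferred from the footnote giving them a Day 21 window. SAP 14.3 keeps all assessments in the listings, so nothing is lost from the data.

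**Conclusion.** The point holds as a minor drafting defect. Taken literally, footnote d misfiles a Visit 11 rating on Day 19 when the second randomized dose was on Day 12 (IndexB+7) or Day 13 (IndexB+6), both within the protocol's tolerance. If tolerance accumulates, IndexB on Day 10 or 11 has the same result for a Visit 11 at IndexB+7.

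The number affected cannot be computed from the documents. Under the assumed rates it is about 0.1-0.3% of completers on the calendar reading and 3-6% on the dose-to-dose reading.

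The effect is confined to completeness and labelling of the BPRS+ and CADSS by-visit summaries. A reader might suspect the efficacy results or a distorted safety contrast. Neither follows: MADRS change from randomized baseline uses Table 14.1-2, which is anchored to IndexB throughout this range, and the misfiling depends on visit dates, with no reason in the documents to expect them to differ by arm.

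**What to change.** In footnote d, end the Day 15 window at IndexB+5 instead of Day 19, and start the Day 21 window at IndexB+6 instead of Day 20, keeping the last double-blind visit as its end. The cost is one line of SAP text and the matching line of code; no new data are needed.

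This gives these two scales the same Day 21 start as the other safety parameters. It does not undo the footnote's extension of the Day 1, Day 8 and Day 15 windows: ratings in the Day 18 range will still be labelled Day 15. That includes the late-dose cases in step 5 of the working, where Visit 11 is only 4 or 5 days after the dose and would move from Day 21 to Day 15. So the gain is one consistent, dose-anchored rule; it does not guarantee that every Visit 11 rating lands in Day 21. If the table's general IndexB+6 start is ever revised, footnote d should take the same revised bound.

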### 9.7.9 Determination of Sample Size

**The originally proposed primary efficacy variable is the change from baseline in the MADRS total score at 1 day after the first dose of treatment. The study was planned to randomize 700 patients assuming SD of 10 points, which provides 99% power to detect a difference of 3.25 points in MADRS total score between rapastinel 450 mg and placebo at a 2-sided significance level of 0.05.**

**While the study was ongoing, various feedbacks were received from the regulatory agencies including the FDA, EMA, and the Japanese regulatory agency. Following the feedbacks, the primary efficacy variable was revised to be the change from baseline in MADRS score at the last visit, Day 21, and included in Amendment 2 of the protocol. At the same time of Amendment 2, a blinded data review was conducted for Studies RAP-MD-01, RAP-MD-02, and RAP-MD-03. The pooled SD for the 3 studies were 7.4, 8.0, and 8.7, respectively, all smaller than the originally assumed 10 points. Sample size was re-calculated using 8.7 as the common SD. The calculation used MMRM model with simulations; it also assumed correlation of 0.5 between the repeated measures and an overall drop-out rate of 15%. To have 90% power, the total sample size required is 360 patients. However, the study had already enrolled more than 390 patients with less than 5% of overall drop-out rate, surpassing the re-estimated sample size of 360 patients. The study enrollment was halted as soon as operationally feasible. The final sample size is approximately 420 patients (210 patients per treatment group).**

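### On the visible text, the SAP's Day 21 window opens one day later than the earliest Visit 11 the protocol allows, so a compliant completer can lack a primary-timepoint MADRS score (minor, subject to footnote e)

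*SAP*

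**What the plan says.** **Protocol.** Section 9.1.2 places visits "4 days following the treatment day, and 7 days following the treatment day". It adds: "If necessary, study visits may be conducted up to 2 days before or after the scheduled visits". The only exceptions are the 24-hour pairs (Visits 2/3, 5/6 and 8/9). It also states "All patients who receive IP must complete Visit 11". The primary endpoint in Section 9.7.5.1 is the MADRS change at end of study.

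**SAP.** Section 8.1 defines the primary endpoint as the MADRS change from baseline to Day 21, analysed on observed cases. In Table 14.1-2 the Day 18 window is ["IndexB ^c +2, IndexB ^c +5"] and the Day 21 window is "Days [IndexB ^c +6, day of final double-blind visit or Early-termination Visit occurring after IndexB ^c +5" (the caret and c mark a footnote). Table 14.1-1, to which the sentence before Table 14.1-2 actually refers, has the same cut.

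**Duplicates.** For two assessments "within the same window, the assessment closest to the target day will be used for analysis" (Section 14.1), with ties going to the later one. Section 8.1 instead takes the last MADRS assessment for the same nominal visit.

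The Day 21 row carries a footnote marker e in both tables. Its text is not in the document as available.

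**The concern.** The protocol's tolerance and the SAP's windows do not meet. A patient can attend every visit within the protocol's limits, be rated at the final visit, and still have nothing in the Day 21 window.

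Two analyses are touched. The primary MMRM would treat that completer as missing at the primary timepoint, although earlier visits stay in the model. The pattern-mixture analysis sets the pattern by the last observed visit, so the same patient becomes a drop-out after Day 18. Day 21 is then the first missing value and receives the full shift of 0 to 8 points, in place of a score that was actually collected.

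The duplicate rules raise a separate problem. Two programmers following different sections could derive different MADRS values from the same records, and the SAP does not settle which is right.

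**Working it through.** **1. Anchor.** Doses are given at Visits 2, 5 and 8 (Protocol 9.4.7). The SAP counts 1 or 2 randomized doses after a lead-in dose (SAP 2.0 and 7.1). IndexB, the second randomized dose, is therefore taken as Visit 8, nominally Day 14. The SAP's target for Day 21 is reproduced: 21 − 14 = IndexB+7.

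**2. Tolerance counted from the Visit 8 dose.**
- Visit 10: 4 ± 2, so +2 to +6.
- Visit 11: 7 ± 2, so +5 to +9.
- Pairs with Visit 10 before Visit 11: 5 × 5 − 3 = 22.

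Three pairs have no Day 21 score under either duplicate rule:

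| Visit 10 | Visit 11 | Day 18 value (closest to +4, tie to later) | Day 21 value |
|---|---|---|---|
| +2 | +5 | Visit 11 | none |
| +3 | +5 | Visit 11 | none |
| +4 | +5 | Visit 10; Visit 11 unused | none |

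**3. Tolerance counted from the Day 0 calendar.** Visit 8 falls on Day 12 to 16 and Visit 11 on Day 19 to 23, giving 25 date pairs with offsets from +3 to +11. Six pairs are at +5 or earlier: (14,19), (15,19), (15,20), (16,19), (16,20) and (16,21). In the last, Visit 11 falls exactly on study Day 21 and is filed as Day 18.

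**4. Where the duplicate rules part.** With Visit 10 at +6 and Visit 11 at +9, both fall in the Day 21 window. Distances from the target are 1 and 2 days, so the closest rule takes Visit 10. A last-in-window rule would take Visit 11. This is 1 of the 22 pairs.

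**5. Effect on power.** From the documents: SD 8.7, correlation 0.5, 210 per arm, drop-out below 5%. Assumed: exactly 5% drop-out spread evenly over six post-randomization visits, compound symmetry, and the share of completers who miss only Day 21. Completers: 0.95 × 420 = 399. The SE comes from the MMRM information matrix, and power = Φ(difference/SE − 1.96). The recalculation states no target difference. The 3.25 points are the original design value, and 3.0 is an assumption.

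| Completers affected (assumed) | SE | Power, 3.25 points | Power, 3.0 points |
|---|---|---|---|
| 0% | 0.863 | 96.4% | 93.5% |
| 1% (4) | 0.866 | 96.4% | 93.4% |
| 2.5% (10) | 0.870 | 96.2% | 93.2% |
| 5% (20) | 0.877 | 96.0% | 92.8% |

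For example, 3.25/0.877 − 1.96 = 1.746 and Φ(1.746) = 96.0%. The loss at 5% affected is 96.4 − 96.0 = 0.4 points, or 93.5 − 92.8 = 0.7 points.

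**6. Effect on the pattern-mixture analysis.** Drop-out below 5% of 420 is at most about 21 patients. Adding 4 or 10 misfiled completers would raise the number imputed at Day 21 by 4/21 = 19% or 10/21 = 48%. At the largest shift, each moves its arm mean by 8/210 = 0.038 points, which cancels if the arms are affected equally.

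**The case against.** The strongest objection is that the finding rests on unseen text. Marker e sits on the Day 21 row. Footnote d, which can be read, also marks Day 21 in Table 14.1-1 and rewrites that window, but only for BPRS+ and CADSS. Footnote e may do something similar for the MADRS. The protocol's visit-by-visit descriptions are blacked out and the restricted addendum is not available, so a tighter limit for Visit 11 could exist there. This stands, and it makes the window point conditional.

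The cut is also defensible as ordinary windowing. The midpoint between +4 and +7 is +5.5, so a score at +5 is nearer the Day 18 target. That is true, but it does not remove the conflict with a final visit the protocol accepts at +5.

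Section 8.1 speaks of nominal visits. If those governed assignment, Visit 11 would stay Day 21. But Section 8.1 settles only duplicates, and Section 14.1 says the windows apply to efficacy.

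The consequence is small. Early visits are allowed only if necessary, and in two of the three schedules the Visit 11 score stays in the model as Day 18. This stands. The +6/+9 schedule is likewise the closest rule working as written; it matters only because the other rule could give a different answer.

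A reader might infer that both documents define the endpoint by the final visit, from "the primary efficacy variable was revised to be the change from baseline in MADRS score at the last visit, Day 21" (SAP 12.0) and "the change from baseline in MADRS score at the last visit, Day 21" (Protocol 9.7.9). Those sentences recount how the sample size was revised. The operative definitions are end of study (Protocol 9.7.5.1) and Day 21 (SAP 8.1). The conflict remains on those texts, but it should not be argued from the sample-size history.

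**Conclusion.** On the visible text the mismatch is real. A compliant completer with a rated Visit 11 can have no Day 21 MADRS: 3 of 22 schedules counted from the dose, or 6 of 25 Visit 8/Visit 11 date pairs on the calendar reading. It rests on IndexB being Visit 8, on the 2-day tolerance applying to Visit 11, and on footnote e not already keeping Visit 11 as Day 21.

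A reader might infer that a corresponding share of patients loses the primary value, or that the treatment comparison is biased or materially underpowered. The documents support neither. The counts are of possible schedules, no attendance frequency is given, and nothing suggests the arms would differ. Even at an assumed 5% of completers, the power loss is about 0.4 to 0.7 percentage points.

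The unreconciled duplicate rules in Sections 8.1 and 14.1 stand on visible text, whatever footnote e says. Severity: minor.

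**What to change.** Before unblinding, confirm footnote e and amend the SAP:

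- In 14.1, state that a completed scheduled Visit 11 MADRS is the Day 21 value and a scheduled Visit 10 MADRS is the Day 18 value.
- Keep date windows for early-termination and unscheduled assessments.
- State one duplicate rule for the MADRS, worded identically in 8.1 and 14.1. Once scheduled visits are assigned by visit, Visits 10 and 11 no longer compete for one slot, so stating a single rule matters more than which one is kept.

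If footnote e already keeps Visit 11 as Day 21, only the duplicate rule needs attention.

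The cost is SAP wording and a small programming change. The downside is that Day 21 values will spread over the days since dose that the protocol already allows (+5 to +9, or wider on the calendar reading).

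Simply opening Day 21 at IndexB+5 is not an adequate substitute. On the calendar reading, 3 of 25 date pairs, (15,19), (16,19) and (16,20), are at +3 or +4 and would still be missed. Counted from the dose, schedules with no Day 18 score would rise from 3 to 7 of 22.

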#### **9.4.2                   Treatments Administered**

The IP will only be administered to eligible patients by a medically qualified person as per the local state regulations. The range of persons who can administer an IV can be a physician, a physician assistant, nurse, or nurse practitioner, etc, depending on the local and/or state law.

IP should be administered after all efficacy and safety assessments with the exception of the post-dose assessments described below. IP will be administered in a “slow bolus” injection to each study patient in an upper extremity vein within approximately 1 to 2 minutes.

During IP administration and until completion of postadministration assessments a licensed physician must be immediately available and in close proximity to the patient(s) to attend to medical emergencies. ***The study center must have the capabilities, in accordance with the applicable country, local, and/or state regulations and standard of care, to resuscitate a patient in the event of a medical emergency.***

The patient should not be discharged from the study center until the following are completed:

- Postadministration vital sign measures (approximately 15 minutes after administration)
- Patient is clinically assessed and determined to not be at increased risk of suicidality in the opinion of the Investigator (or medically qualified subinvestigator)
- Patient is assessed for mental status and is determined to be free of perceptual disturbances or other conditions that would deem them not ready for discharge from the study center, in the opinion of the Investigator (or medically qualified subinvestigator)
- A physician licensed in the state (Investigator or subinvestigator) determines that they are medically able to leave the study center and provides written sign-off not less than 15 minutes following administration (see IV Administration and Discharge Notes document in Program Reference Manual)

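### As written, SAP 14.1 picks post-dose over same-day pre-dose vital signs at Days 7 and 14, and its Baseline row does not match the baseline text

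*SAP*

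**What the plan says.** SAP 14.1 states that Table 14.1-1 applies to "all safety analyses where baseline is the last nonmissing assessment before the first dose of DB IP in the placebo lead-in period". The windows in that table are defined by date, with no clock time and no pre-dose or post-dose flag.

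- The Baseline row reads "Last record on or before Index0", where Index0 is the date of the lead-in placebo dose.
- The Day 7 window is the single date IndexA, and the footnote gives "IndexA: Date of first randomized dose or Index0 + 7 for patients who did not receive any randomized dose".
- The Day 14 window is the single date IndexB, the date of the second randomized dose, or IndexA + 7 if that dose was not given.
- After Table 14.1-2, the SAP says that when a window holds several records the one closest to the target day is used, and then: "if there are 2 closest assessments with the same number of days from the scheduled day, the later one will be used for analysis".

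SAP 14.3, on repeated safety assessments, takes as baseline the final non-missing value before double-blind treatment starts. It also says that all postbaseline values enter the PCS determinations and that all assessments are listed.

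Protocol 9.4.2 sets the order on dosing days: "IP should be administered after all efficacy and safety assessments with the exception of the post-dose assessments described below". The post-dose list includes vital signs about 15 minutes after administration. Protocol 9.4.7 gives the dosing visits as 2, 5 and 8, which are Days 0, 7 and 14 in the SAP.

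**The concern.** A dosing day can carry two vital-sign readings on the same date, one before and one about 15 minutes after a bolus injection. They answer different questions. The first describes the patient's state a week after the previous dose. The second describes the acute response to the dose just given. A rule that sees only the date treats them as duplicates and keeps the later one.

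The by-visit vital-sign summary at Days 7 and 14 is therefore at stake. The pre-dose value would disappear from it, and a same-day change could not be formed from the windowed data. Day 7 matters most. It follows a week in which every patient received placebo, but its selected value in the rapastinel arm would be taken after the first active injection. The SAP reports adverse events separately for the lead-in and randomized periods, so a reader may expect the same separation for vital signs.

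The Baseline row is a separate matter. Taken alone, it would accept a reading after the Day 0 injection, which the text above the table and 14.3 do not allow.

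**Working it through.** The plan gives no figure to reproduce. The check is to apply the selection rule as written.

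**Inputs**
- Windows, index dates and tie rule: SAP 14.1.
- Order of assessments and injection, and the reading at about 15 minutes: Protocol 9.4.2.
- Dosing on Days 0, 7 and 14: Protocol 9.4.7, with the SAP index dates.
- Assumed: one pre-dose reading on each dosing day. Protocol 9.2 puts safety assessments at every visit and 9.4.2 puts them before dosing, but the schedule that would confirm vital signs is redacted.
- Assumed: one reading at each visit without dosing.
- Number per arm: about 210 (SAP 12.0).

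**Step 1. Distance to target.** On Day 7 the target is IndexA and both readings fall on IndexA, so each distance is IndexA − IndexA = 0 days. Day 14 gives IndexB − IndexB = 0 for both. These windows are one date wide, so any two records in them tie and the tie rule always decides.

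**Step 2. Selection.**

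| Row | Records available | Chosen as written | Chosen when limited to pre-dose records on dosing dates |
|---|---|---|---|
| Day 7 | pre-dose, post-dose | post-dose | pre-dose |
| Day 14 | pre-dose, post-dose | post-dose | pre-dose |
| Days 1, 4, 8, 11, 15, 18, 21 | one each | that record | unchanged |

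**Step 3. Baseline.** This row takes the last record and does not use closeness to target. Read alone, it returns the reading after the Day 0 placebo injection. The 14.1 text and 14.3 both return the pre-dose reading. Two explicit statements stand against one loosely worded row.

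**Step 4. Who is affected.** At Day 7, about 210 values in the rapastinel arm would follow active drug. The placebo arm's values would follow placebo. The pre-dose reading would drop out of the Day 7 and Day 14 summaries in both arms, up to 2 × 210 = 420 patients.

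**Step 5. What is not affected.** PCS determinations and listings use every postbaseline value (SAP 14.3). Efficacy assessments precede the injection (Protocol 9.4.2), so the windows do not exchange a pre-dose MADRS for a post-dose one. Vital signs are the only post-dose measurement with a stated time in the visible text, so the point is not shown for laboratory tests or ECGs.

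**The case against.** The strongest reply is that the relevant text cannot be seen. The vital-signs analysis section of the SAP and the visit schedule are redacted, and either may define pre-dose and post-dose readings as separate time points. That would be compatible with a table that assigns dates to visits, with ties resolved within each time point. This stands, and it makes the finding conditional. It does not remove the need for alignment. Table 14.1-1 claims all safety analyses, and its footnote d gives special windows for BPRS+ and CADSS, but no visible exception covers vital signs.

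The tie sentence also follows Table 14.1-2, the efficacy table. Its wording is general and no other tie rule for Table 14.1-1 is visible, so applying it to safety is reasonable though not explicit.

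A reader might infer three stronger conclusions, which the documents do not support:

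- *That every patient's baseline is a post-injection value.* The 14.1 text and 14.3 both require a value before the first double-blind dose. The Day 0 injection is placebo for everyone, so even the literal row would bring in no drug effect.
- *That the comparison between arms is biased.* Both arms would contribute post-dose values, measured against the same kind of baseline. The loss is the pre-dose summary and the same-day reference.
- *That acute abnormal values would be hidden.* They still enter the PCS determinations and the listings.

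It is also fair to say that Table 14.1-1 does not itself label Day 7 as lead-in. It defines that date as the first randomized dose.

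**Conclusion.** The point holds in limited form and is minor. Followed literally, SAP 14.1 selects the post-dose vital signs at Days 7 and 14, in place of the same-day pre-dose reading. In about 210 rapastinel patients the Day 7 value would then come after the first active injection. The Baseline row conflicts in wording with the 14.1 text and 14.3. Those texts protect the baseline, so the row needs reconciling but does not show a wrong baseline.

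This rests on three assumptions: a pre-dose vital-sign reading is taken on dosing days, the tie sentence covers the safety table, and the redacted section does not already separate the two readings. Only by-visit descriptive summaries of vital signs are exposed.

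**What to change.** In SAP 14.1:

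1. State that pre-dose and post-dose vital signs on a dosing date are separate time points, and that the closest-record and tie rules apply within each.
2. Assign post-dose readings on IndexA to the randomized period.
3. Change the Baseline row of Table 14.1-1 to the last record before the first double-blind dose, to match the 14.1 text and 14.3.
4. If the redacted vital-signs section already separates the readings, cross-refer to it so that the two agree.

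A table of post-dose minus same-day pre-dose change by arm and dose would be a useful but optional addition.

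The cost is a few lines of SAP text and minor programming, provided that vital-sign records carry a clock time or a pre/post-dose flag. Protocol 9.4.12 confirms that injection date and time are captured. Nothing visible confirms the same for vital signs, so that should be checked first.
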